Purpose of the Study

Aim 1: Examine the feasibility and acceptability of a national, low-cost, community-based, peer-led, weight loss program (Take Off Pounds Sensibly, TOPS) for overweight and obese African American breast cancer survivors in the local chapter of a national African American breast cancer support group (Sisters Network Triangle North Carolina, SNTNC).

Hypothesis 1: The TOPS format, materials, and content will be feasible and acceptable to overweight and obese African American breast cancer survivors in SNTNC.

Aim 2: Assess the weight change of overweight and obese African American breast cancer survivors after 6 months in the TOPS program to gather data for sample size calculations for a future RCT.

Hypothesis 2: Overweight and obese African American breast cancer survivors in TOPS will lose 5% of their initial body weight, which is clinically significant, within 6 months.

Background & Significance

Mounting evidence links overweight and obesity to cancer. In women diagnosed with breast cancer, obesity contributes to both breast cancer-specific and cardiovascular disease mortality. In one study, breast cancer survivors diagnosed at ≥66 years were more likely to die from cardiovascular disease than breast cancer. Therefore, obesity also plays a role in their cardiovascular mortality. Unfortunately, breast cancer treatment can exacerbate these issues because it may be associated with weight gain; increased cardiovascular events; and decreased physical function.

Compared to the general population, African American women have higher rates of overweight and obesity among those with and without breast cancer; gain more weight after they are diagnosed with breast cancer; and have worse outcomes for breast cancer mortality and cardiovascular disease. For women diagnosed with breast cancer, interventions targeting diet, weight loss, and physical activity have been associated with clinically significant weight loss; decreased mortality; reduced risk of breast cancer recurrence; and fewer cardiovascular events. Unfortunately, African American women lose less weight than other groups in standard weight loss programs.

In one randomized controlled trial, African American breast cancer survivors in an expert-led intervention – weekly didactic sessions, twice weekly supervised exercise sessions, and twice weekly text messages with community-based nutritionists and exercise trainers – lost an average of 3.6% of their weight and 44% of participants lost at least 5% of their initial weight. However, personnel increase the intervention costs, and there is no infrastructure for nationwide dissemination of this program. To decrease adverse clinical and mortality outcomes among African American breast cancer survivors, a weight management intervention with scalable infrastructure that can be implemented in low-resource settings is needed.

A national, low-cost, community-based, peer-led weight loss program (Take Off Pounds Sensibly, TOPS) can fill this unmet need. TOPS is a nonprofit, evidence-based weight loss program with a national infrastructure that offers a pragmatic option to help women diagnosed with breast cancer manage their weight. First, it includes all of the components that the NIH asserts should be included in "safe and effective" weight loss programs. Second, [name] retrospective analyses showed: 1) TOPS participants lose a clinically significant amount of weight and maintain the loss for up to 7 years. Third, its peer-led, community-based structure ensures each chapter is contextually tailored for its members. For instance, in a successful pilot study, [name] started three TOPS chapters specifically for older African American women; and one chapter continued for almost 8 years after the study ended in 2012 (until the COVID-19 pandemic). Fourth, TOPS costs participants less than \$100 per year. Finally, TOPS's nationwide infrastructure, with chapters in every state, can facilitate dissemination and implementation. However, because women with breast cancer have greater psychosocial stressors, including time-consuming treatment regimens and fear of recurrence, they may need different levels of support than those offered in standard TOPS chapters, and this study can reveal those elements and provide preliminary data for a future randomized controlled trial (RCT).

Sisters Network Triangle North Carolina (SNTNC) is an affiliate chapter of Sisters Network, Inc., a national African American breast cancer survivorship organization. SNTNC was established in 2003. Prior to the COVID-19 pandemic, SNTNC held separate monthly meetings in both Raleigh and Durham, NC. Since the pandemic, SNTNC combined the Raleigh and Durham meetings into one monthly virtual Zoom meeting. In the past, SNTNC has participated in research projects about survivorship, barriers to care, and treatment adherence.

For African American women diagnosed with breast cancer, our long-term goals are to decrease cancer-specific, cardiovascular, and all-cause mortality. The objective of this proposal is to conduct formative research to determine if the format and materials of the TOPS program are feasible and acceptable to overweight and obese African American breast cancer survivors. This project seeks to address the health disparities of overweight and obesity and cardiovascular disease among African American breast cancer survivors and benefits from the following: 1) the existing infrastructure of the SNTNC, the Raleigh/Durham chapter of a national African American breast cancer survivorship organization; 2) the successful weight loss of participants in the TOPS program; and 3) [name] experience with studies of the TOPS program. The outcomes will be a) determination of the feasibility and acceptability of the TOPS program by women of SNTNC; b) recommendations the women of SNTNC have to modify the program to make it relevant to their experiences; and c) preliminary weight change data for sample size calculations for a future RCT of TOPS for weight change among this population.

This work will develop the evidence base for a scalable weight loss intervention among African American breast cancer survivors – a population with poor breast cancer and cardiovascular outcomes. If effective, these results have the potential to help increase both the survival and quality of life for this population.

Design & Procedures

Research design. Part of the study design will be the further development of study documents including TOPS programs, survey questions, and focus group scripts. The documents will not be used until full IRB approval is granted for the final drafts via amendments.

This project will be a six-month single arm study that will use qualitative and quantitative methods to measure the feasibility and acceptability of the TOPS program among African American breast cancer survivors. Qualitative methods will collect data about participants' perceptions of the program and suggestions for modification to make it relevant to them and their experiences. We will conduct up to five focus groups and up to 10 in-depth interviews. Quantitative methods will measure recruitment, retention, and weight change.

Subjects. Overweight and obese African American breast cancer survivors in the Sisters Network Triangle North Carolina (SNTNC).

Inclusion criteria:

18 years old and over

Women diagnosed with breast cancer

BMI ≥ 25 kg/m2 after completion of primary therapy (surgery, radiation, adjuvant or neo-adjuvant chemotherapy)

Regular access to a computer and internet

Exclusion criteria:

Under 18 years old

Have not had a breast cancer diagnosis

Currently undergoing infusion chemo therapy treatment

Do not have access to a computer and the internet

BMI is less than 25 kg/m2

Women whose oncology providers do not agree with their participation in a weight loss program Participating in another weight loss program

If on insulin or sulfonylureas and provider does not agree to help manage their medications. They will need a signed provider permission form.

Study Setting. The study will be conducted via Zoom. Since the COVID-19 pandemic, SNTNC has met online. Approximately 50 to 60 women participate each month. Thus, the group is used to meeting in the virtual space. Duration. Subjects will join newly formed TOPS chapters for 6 months. Then, they will be asked to participate in focus groups to collect data about their perceptions of the TOPS program.

Recruitment and Screening. The study will enroll up to 50 women, who will be recruited through the Sisters Network Triangle North Carolina (SNTNC). [name], MSN, RN, is a Patient Navigator at the Duke Cancer Center. She is also the co-founder, past president, and current program manager for SNTNC and she is an enthusiastic proponent of this project. She will assist with the recruiting efforts.

[name] will attend up to two of the monthly SNTNC meetings, and she and [name] will present an information session about the study via a Zoom meeting. Individuals will be invited to contact the study team to determine if they are either overweight or obese based on self-reported height and weight and calculated BMI. If women qualify based on BMI, they will be asked pre-screening questions in REDCap to determine if they are eligible to participate in the study. Based on [name] extensive experience recruiting participants for previous studies, we believe we will be able to complete the recruitment phase within two months.

Participants that complete the screening questions and note that they are on insulin (such as, U-100, U-200, U-300, ultra long acting, pre-mix (i.e. 70/30, 75/25), U-500 (ultraconcentrated), inhaled insulin) or sulfonylureas (such as, glyburide [DiaBeta, Glynase, PresTab, Micronase], glipizide [Glipizide XL, Glucotrol, Glucotrol XL], glimepiride [Amaryl], tolazamide [Tolinase], or tolbutamide [Orinase]) they will need to get a permission form signed by their provider. The form will be sent via email to the participant to take to their provider. The permission form will be used to notify the patients provider that they would like to participate in a weight loss study which may cause changes to their diabetes medications. The PI will not be responsible for managing their medications so the participants' provider must sign the form stating that they will agree to help manage the participants medications if needed. If the participant does not get a signed permission form or their provider does not agree to help manage their medications they will be ineligible to continue with the study. The forms will be collected, uploaded, and noted in REDCap.

Participants that attend the Zoom information session and are interested in participating in the study will be sent a link to our REDCap project. They will be able to review information about the study such as why we are doing the study, risks/benefits, and determine if they would like to continue by answering some questions. They will provide some information to identify themselves and to determine eligibility. Once eligible, participants will be able to review the e-consent. They can have as much time as needed to review, ask the study team questions via phone or email, and sign using an e-signature. After they sign they will be sent a copy of the e-consent via email that they provide. If they are ineligible, they will not be able to continue on to the e-consent.

Intervention. Participants will be invited to join new chapters of the TOPS weight loss program created for the study. Each participant will be offered a free one-year membership in the TOPS program. Participants will receive the "TOPS Plus" new member packet—one-year membership in a local TOPS chapter; My Day One: A Ready-Set-Go Guide for Healthy Living is a 24-page booklet of weight loss basics with a six-week lesson plan; a one year subscription to TOPS News, a bimonthly magazine published exclusively for TOPS members; Real Life: The Hands-on, Pounds-off Guide is a 304-page weight management lifestyle guide; Food Exchange Cards; TheraBands® Resistance Bands; My Real Progress, a 12-week food and fitness journal. TOPS Usual Procedures. The TOPS program usually consists of weekly private weigh-ins on the chapter scale, where the weight recorder notes each person's weight on their individual Weight Chart. Then, there is a group meeting, where members receive educational information on topics such as healthy eating, exercise, or behavior modification. Participants usually get a "provider-approved" weight goal. Modified COVID-19 Procedures. Because of social distancing requirements due to the pandemic, we will have to modify the usual procedures. The study will provide each participant with a scale, and members will provide the weight recorder with their weights each

week. The weight recorder will still record each person's weight on their individual Weight Chart. We will also set an initial weight loss goal of 5% of initial weight, which is considered clinically significant.

Additional Opportunity:

There is an additional opportunity for some participants to become a TOPS leader. This weight loss program requires peer leadership, which means one member of each group will be the leader. This involves reading the materials ahead of time and taking a training on TOPS leadership. Participants will receive an additional compensation for each training module completed to become a TOPS leaders.

Data collection. Focus groups and interviews. All individuals who enroll in the study will be invited to participate in 6 month focus groups and interviews, even if they did not remain in the program. Groups will be led by an experienced moderator and last for 60-90 minutes using open-ended questions to elicit the most information. Focus groups will have up to 6 participants and will be conducted via Zoom by the Behavioral Health and Survey Research (BHSR) Core, led by [name], MPH. We will conduct up to 10 individual interviews with those who are unable to participate in the focus groups. The interviews will include the same themes as the focus groups. Evidence suggests that data saturation can occur within 12 interactions, with primary themes arising as early as six. In this way, we will be able to discover factors associated with program continuation and withdrawal. Focus groups and interviews will be taped and transcribed. Both [name]'s and [name]'s previous experiences with SNTNC have established these as acceptable forms of assessment with this group. All interviews will be audio recorded (via Zoom) and transcribed. All of the patient information will be stored in a secure, shared Duke drive that only the study personnel will have access to. The focus groups will be recorded and stored securely on Duke's Zoom platform, participants will be provided with a password to enter the virtual meeting. Audio will be shared to Duke Box. Notes about the interview, transcripts, and audio will be stored in Duke Box and stored in study records for at least six years after the study is done. After six years, we will destroy the records, or we will remove all information identifying participants.

Survey: All individuals who enroll in the study will be invited to complete a brief survey about their experience at the 6 month interval.

Focus group and interview guide development. Focus group and interview guides will be developed using the Framework for Reporting Adaptations and Modifications – Enhanced (FRAME), which is typically used to retrospectively document modifications that occurred during implementation. In this case, we will use FRAME to guide questions for prospective adaptations for our population of interest. Instead of asking, "What is the nature of content modifications?" we will offer options for possible modifications, such as removing, substituting, or adding elements. Focus groups and interviews will inform the adaptation and implementation of the TOPS program for African American breast cancer survivors. Weight change. Weight change will be calculated at 3 and 6 months as percentage change from initial weight. If the pandemic restrictions allow and participants are comfortable, we can consider study visits for data collection. However, we plan to provide participants with smart scales to transmit data to a secure application.

Risk/Benefit Assessment

There is minimal risk to the subjects. Weight loss has been shown to be safe in obese, older individuals. Additionally, this study will recruit participants into Take Off Pounds Sensibly (TOPS), a nationally available, community-based, peer-led weight loss program. The TOPS program is being used in non-medical settings throughout the United States and Canada and poses minimal risk to participants. Individuals must have a body mass index of 25 or greater to participate in the current study. The minimal risk to human subjects for participation in this study is greatly outweighed by potential health benefits that may accrue participants and by the importance of the scientific knowledge that may reasonable be expected to result from this work.

Data Analysis & Statistical Considerations

Focus groups. We will import all transcripts into the Nvivo software to facilitate organization and analysis. We will use a 5-stage approach to conduct thematic analysis (familiarization; identifying a thematic framework; indexing; charting, and interpretation). Experienced qualitative researchers from the BHSR core will work with the study team to conduct the analysis. Familiarization will involve the entire research team reviewing 2-3 transcripts to identify initial coding themes to become familiar with the data. Identified themes will be used as the initial coding framework to conduct line by line coding of a single transcript. The team will meet to discuss the transcript and modify the initial framework. Next, two researchers will code the remaining transcripts. Coding will include memos for each transcript to annotated coders questions, decision about the data, and reflections on analysis. Each coder will also create an overview memo to collect observations that cut across transcripts during the coding process. After coding, the team will meet to discuss themes, sort codes, and restructure the initial framework as similarities and differences are identified. In the final stage, the team will identify major themes and associated quotes to summarize the results. We will also conduct member checking where we will ask providers and patients interviewed to provide feedback on the summarized data.

Weight change. Weight change will be calculated as last observation carried forward and completers' analyses. For both analyses, weight change will be calculated as difference between baseline weight at 3 and 6 months and as a percentage of initial weight. Weight change will also be categorized in the following groups: weight loss 0 to <5%; weight loss ≥5%; and weight gain.

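### Does Hypothesis 2 need rewriting because its 5% weight loss is not defined as a group mean or as a share of women?

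*Protocol*

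**What the plan says.** Under *Purpose of the Study*, Aim 2 is to assess weight change "after 6 months in the TOPS program to gather data for sample size calculations for a future RCT". Hypothesis 2 adds that the women "will lose 5% of their initial body weight, which is clinically significant, within 6 months".

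Elsewhere 5% belongs to the individual woman. Under *Design & Procedures* (Intervention), the protocol states: "We will also set an initial weight loss goal of 5% of initial weight, which is considered clinically significant". Under *Data Analysis & Statistical Considerations* (Weight change), it is a cut-off between categories: "weight loss 0 to <5%; weight loss ≥5%; and weight gain". The same paragraph calculates change at 3 and 6 months, in absolute terms and as a percentage of initial weight, by last observation carried forward (LOCF) and in completers. It names no leading analysis and no target share.

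*Background & Significance* gives one numerical comparator, an expert-led programme with supervised exercise in African American breast cancer survivors, who "lost an average of 3.6% of their weight and 44% of participants lost at least 5% of their initial weight". It also says that "African American women lose less weight than other groups in standard weight loss programs". In favour of TOPS it cites retrospective analyses in which "TOPS participants lose a clinically significant amount of weight and maintain the loss for up to 7 years", without a figure.

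**The concern.** A hypothesis should be capable of being scored. This one can be read as a mean loss of 5%, or as women reaching 5% with no proportion given. The cited comparator shows how far the readings can part: against Hypothesis 2 it would fail on the mean and have no verdict on the share.

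Read as a mean, the target is 1.4 points above a result from a more intensive programme, so a TOPS chapter that did equally well would probably be reported as missing its hypothesis. LOCF and completers' results can also fall on opposite sides of 5%. If the meaning were chosen after the data were seen, the choice could favour whichever result looked better. A further worry is that the later trial might be planned on 5% when the truth is nearer 3.6%.

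**Working it through.** The protocol gives no SD, dropout rate, power or precision calculation, so there is no stated figure to reproduce.

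**Inputs from the protocol:** target 5%; comparator mean 3.6% and 44% at 5% or more; enrolment up to 50.

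**Assumptions:** normality for the implied SD; SD 5% as a lower alternative; dropout 20% to 30%; last observed loss in dropouts 0 to 2%.

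**1. SD implied by the comparator.** If 44% lie at or above 5% and the mean is 3.6%, then SD = (5 − 3.6)/z(0.56) = 9.27%. Rounding of 3.6% and 44% alone lets this run from about 8.2% to 10.5%.

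**2. Chance that the observed mean reaches 5% if the true mean is 3.6%, n = 50.**

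| SD | SE = SD/√50 | P(mean ≥ 5%) | 95% CI half-width |
|---|---|---|---|
| 5% (assumed) | 0.71 | 0.02 | 1.4 points |
| 9.27% (implied) | 1.31 | 0.14 | 2.6 points |

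With n = 30 the probabilities are 0.06 and 0.20.

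**3. Share reading, true share 44%, n = 50.** P(at least 25 of 50 reach 5%) = 0.24; P(more than half) = 0.16. The one-half threshold is an illustration; the protocol sets none.

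**4. LOCF against completers.** LOCF mean = (1 − d) × completer mean + d × last observed loss in dropouts. For a completer mean of 5.0%:
- d = 0.2, dropouts at 2%: 0.8 × 5 + 0.2 × 2 = 4.4%
- d = 0.3, dropouts at 0%: 0.7 × 5 + 0.3 × 0 = 3.5%

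**5. Agreement of four 6-month results** (mean, and share of at least half, each by LOCF and in completers). Simulation with n = 50, dropout 20% to 30%, dropouts at about 1% loss, SD 5% to 9.27%. The four disagree on whether 5% was met in about 11% to 29% of trials at a completer mean of 3.6%, 53% to 59% at 5%, and 59% to 86% at 6%.

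**6. What depends on the answer.** Set beside the text:
- Aim 2 is met by collecting the data. *Background & Significance* likewise lists preliminary weight change data as the outcome. No rule to proceed or stop is tied to 5%.
- The enrolment limit of 50 is not derived from 5%.
- The aim says after 6 months, and the analysis calculates change only at 3 and 6 months. The 3-month results therefore do not answer the hypothesis, and no analysis of ever having reached 5% on a weekly weight is planned. The difference between *within* and *after* has no analysis attached to it.
- The later trial is to be sized from the observed data. A trial is also sized on a difference between arms, whereas 5% and 3.6% are changes within one arm. Comparing their squares, (3.6/5)² = 0.52, therefore does not describe anything the protocol plans.

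**The case for a change.** The strongest case for a change is that the ambiguity sits in the protocol's own hypothesis, that the open choices can reverse the answer (step 5), and that the cure is a sentence. A pilot that matched the comparator could be described as a failure on one reading and be beyond judgement on another.

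Part of this stands. The hypothesis does not name its summary, and as a mean it is optimistic. But optimism is not contradiction. The protocol points to TOPS data showing clinically significant loss, and it equates that term with 5%; those data carry no figure and are not said to come from this population. The comparator's follow-up time is not given, so 3.6% is not known to be a 6-month result. The remark about lower loss compares African American women with other groups and does not imply a loss below 3.6%.

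Nor is the cure neutral. One could lead with the mean, which serves planning directly, or with the share reaching 5%, which fits the individual goal. Counting every enrolled woman without a 6-month weight as not reaching 5% would add a third treatment of missing data to the two already planned. Statisticians would reasonably differ on these choices, and the results of the present plan allow either summary to be read.

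**Conclusion.** No change is called for. The wording gap is real but small: at 6 months, on the percentage scale, what stays open is mean or share, and LOCF or completers. The plan calculates the quantities needed for all four results, so a report that follows it shows them side by side, and any disagreement between LOCF and completers is visible to the reader. Stating which one leads is commonly left to the SAP, which is not shown here.

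As a mean, the 5% target would probably be missed by a programme only as good as the comparator (chance of reaching it 0.02 to 0.14 with 50 women). That affects how one sentence of the report reads. It alters neither the data collected nor the estimates passed to the later trial. The upper probability rests on normality and on rounded published figures, the lower on an assumed SD of 5%, and both on all 50 women being enrolled and analysed. The conclusion does not depend on these values; it depends on nothing in the protocol being decided by whether 5% is reached.

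### The protocol does not say which of two sources supplies the 3- and 6-month weights, and does not request those weights from women who leave TOPS

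*Protocol*

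**What the plan says.** **Weight sources.** Two are described, in different sections.

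- Intervention, modified COVID-19 procedures: "The study will provide each participant with a scale", and "members will provide the weight recorder with their weights each" week. The recorder enters them on each woman's chart.
- Data collection, weight change: "we plan to provide participants with smart scales to transmit data to a secure application". Visits are a conditional alternative: "If the pandemic restrictions allow and participants are comfortable, we can consider study visits for data collection".

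**Time points.** The same weight paragraph states: "Weight change will be calculated at 3 and 6 months as percentage change from initial weight".

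**Contact with leavers.** Under Data collection, the focus groups and interviews are open to every enrolled woman, "even if they did not remain in the program". The survey is equally broad: "All individuals who enroll in the study will be invited to complete a brief survey about their experience at the 6 month interval".

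**Analysis.** Under Data Analysis & Statistical Considerations, weight change is analysed in two ways: by carrying the last observation forward, and in completers.

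**Purpose.** Aim 2 is to assess weight change after 6 months so that a future RCT can be sized. Hypothesis 2 sets a 5% loss.

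**The concern.** The weekly report to the chapter recorder is the only weight route with a stated frequency and a named recipient, and it is worded for chapter members. The smart-scale route is worded for participants, but it has no weighing schedule and no request attached. A reader cannot tell which of the two provides the analysed weights.

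The gap matters most for women who leave. The protocol expects some to leave and plans to contact them at month 6 for their views, yet it does not extend the weight measurement to them in the same way. Women who leave may well differ in weight change from those who stay. If their 6-month weights are not sought, the 6-month result rests on an older weight or on the stayers alone. A woman who leaves before month 3 is affected at both time points. An estimate used to size a later trial would carry that error forward.

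**Working it through.** The protocol gives no retention rate, standard deviation or sample size derivation, so there is no stated figure to reproduce. The check is a comparison of the text, followed by arithmetic on labelled assumptions.

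**1. What happens to a woman who leaves TOPS**

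- Weekly report to the recorder: worded for members; no provision after leaving.
- Smart scale: planned for participants whatever their membership; yields a weight only if she uses it; no request at month 3 or 6.
- Study visit: may be considered; not committed to.
- Focus group or interview at 6 months: leavers expressly invited.
- Survey at 6 months: all enrolled women invited; no weight item mentioned.
- Analysis without a 6-month weight: last weight carried forward, or woman omitted.

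No sentence requests a 3- or 6-month weight from a leaver, and none says that her weight collection ends.

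**2. Shift in the all-women mean**

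Input from the protocol: "The study will enroll up to 50 women"; take N = 50. Assumptions: a share p of 20% to 40% leaves without a 6-month weight, and their true mean change differs by d = 1 to 3 percentage points from the value substituted.

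Women affected = p × N: 0.20 × 50 = 10; 0.40 × 50 = 20.

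Shift = p × d:

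- smallest: 0.20 × 1 = 0.2 points
- largest: 0.40 × 3 = 1.2 points

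Relative to the 5% target: 0.2 / 5 = 4%; 1.2 / 5 = 24%.

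**3. One worked scenario**

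Assumptions, none from the protocol: stayers' mean change −5%, leavers' last recorded weight −2%, leavers' true 6-month change 0%. The completers' mean is −5.0% in both cases.

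- 10 leavers: carried forward (40 × −5 + 10 × −2) / 50 = −4.4%; all women weighed (40 × −5 + 10 × 0) / 50 = −4.0%. Loss is overstated by 0.4 points (carried forward) and 1.0 point (completers).
- 20 leavers: carried forward (30 × −5 + 20 × −2) / 50 = −3.8%; all women weighed (30 × −5 + 20 × 0) / 50 = −3.0%. Loss is overstated by 0.8 and 2.0 points.

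The completers' errors exceed what the same p gives in step 2 because omitting leavers in effect gives them the stayers' mean, here 5 points from their true value. With other assumptions the sign could reverse.

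**4. Share losing at least 5%**

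Assume that 44% of stayers reach this threshold, borrowed from the expert-led trial in Background & Significance. The bounds count all unweighed leavers as failures, then as successes.

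- 10 leavers: 0.44 × 40 ≈ 18; bounds 18/50 = 36% and 28/50 = 56%.
- 20 leavers: 0.44 × 30 ≈ 13; bounds 13/50 = 26% and 33/50 = 66%.

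**The case against.** The strongest reply is that the weekly report is a TOPS programme procedure adapted for the pandemic, and that the research measurement is the smart scale, which does not depend on membership. A reader might infer from the members' wording that weight collection stops when a woman leaves, so that leavers have no 3- or 6-month weight. The documents do not support that. The smart scale is planned for participants, study visits remain possible, and no passage states a stopping rule. Each woman is also offered a one-year membership, and the protocol does not say when someone who stops attending ceases to be a member.

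It would likewise go too far to say that a leaver keeps her scale, since the text says only that one is provided. Nor is weight the sole quantitative outcome: recruitment and retention are also measured.

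A second reply is that the survey questions are still to be developed and approved by amendment, so a weight item may yet appear, and that an SAP may exist. The first part is fair: the final survey cannot be judged. But an SAP can only choose how to treat missing weights. It cannot recover weights that nobody requested. Who is weighed, when and by what route is a protocol procedure.

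A third reply is that the magnitude is assumed throughout, and that its lower end is small. With an assumed SD of 4 to 6 points and 50 women, the standard error is 4/√50 ≈ 0.57 to 6/√50 ≈ 0.85 points. A 0.2-point shift is minor beside that; a 1.2-point shift is not. The calculation also treats every leaver as unweighed, although some may use the scale unprompted. These limits stand, and the figures are illustrations.

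**Conclusion.** The point holds in a limited form. The protocol names two weight sources without saying which supplies the 3- and 6-month values, and it does not request those values from women who leave TOPS, although it plans to contact the same women at month 6. Followed as written, a leaver's weight depends on an unprompted scale reading or an optional visit; failing that, it is carried forward or she is omitted.

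The resulting bias in the Aim 2 estimate has unknown size and direction. The range of 0.2 to 1.2 points (4% to 24% of the 5% target) rests on three assumptions: 20% to 40% of women leave, none of them provides a 6-month weight, and their true change differs by 1 to 3 points from the substituted value. For a single-arm pilot this is an inexpensive improvement worth making, not a flaw that invalidates the study. It should be settled before follow-up ends, because an unmeasured weight cannot be recovered later.

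**What to change.** In the weight-change paragraph under Data collection:

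- Name the source of the 3- and 6-month weights: recorder reports, smart-scale transmissions, or one with the other as a stated back-up.
- State that every enrolled woman is asked for a scale reading at months 3 and 6, whether or not she is still in a TOPS chapter, and that she has the study scale available for this.
- Collect the month-6 reading at the contact that already carries the survey and the focus-group or interview invitation.
- Use these observed weights in the 3- and 6-month summaries of all enrolled women, leaving carry-forward for those who still have no reading.

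The cost is one prompt at month 3, one survey item at month 6, and a sentence in the protocol and the consent form. Some leavers will not reply, so missing weights will be reduced but not removed.
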